1.0 TRIAL SUMMARY

Abbreviated Title	Imaging the flare response from pembrolizumab with FDG PET/CT.
Trial Phase	Correlative
Clinical Indication	Patients with advanced metastatic melanoma who are starting pembrolizumab.
Trial Type	Prospective observational cohort study.
Type of control	No control.
Route of administration	n/a
Trial Blinding	None
Treatment Groups	n/a
Number of trial subjects	30 evaluable subjects
Estimated enrollment period	1 year
Estimated duration of trial	2 years
Duration of Participation	6 months
Estimated average length of treatment per patient	n/a

2.0 TRIAL DESIGN

2.1 Trial Design

This is a single institution, prospective, observational cohort study of FDG PET/CT as an early measure of response in patients with advanced metastatic melanoma scheduled to start pembrolizumab. Patients may participate in this study if they are greater than 18 years of age; most participants will be receiving care at the clinical practices of the University of Pennsylvania. Patients that may meet eligibility criteria will be approached about study participation regardless of race or ethnic background.

We anticipate enrolling up to 35 participants with metastatic melanoma who meet eligibility requirements for this study. The target accrual goal is to reach 30 evaluable patients, defined as those who complete two (Baseline and 1st Post-therapy) of the three planned FDG PET/CT scans. Thus, accrual is estimated to occur over approximately 1 year.

FDG PET/CT imaging will be used to evaluate glycolytic activity at sites of metastatic disease using the FDA approved clinical Positron Emission Tomography (PET) radiotracer, [¹⁸F]Fluorodeoxyglucose (FDG). Study imaging will be performed in a manner identical to standard clinical FDG PET/CT imaging procedures used at the Hospital of the University of Pennsylvania using a dedicated whole-body PET/CT scanner. For each PET scan static images from the vertex of the skull to toes will be acquired approximately 60 minutes after injection of FDG. Imaging data will be processed as per standard protocol. The study will be performed under the regulatory approval of the Penn Institutional Review Board (IRB).

A total of three FDG PET/CT exams will be performed as follows:

- **Baseline:** A restaging FDG PET/CT will be obtained no more than 4 weeks prior to initiation of pembrolizumab to assess baseline, pre-therapy tumor glycolytic activity. This exam will be obtained for study purposes, although in some cases it may be obtained as clinical standard of care for restaging of disease prior to initiation of a new line of therapy. If this exam is obtained as clinical standard of care, it may occur prior to consent and enrollment in this study.
- **1st Post-therapy:** at approximately 3 weeks (\pm 3 weeks) following the start of pembrolizumab, a post-therapy FDG PET/CT will be obtained. This exam will be obtained for study purposes, to assess glycolytic activity at sites of metastatic disease at an early time-point.
- **2nd Post-therapy:** When clinically indicated, as per the judgment of the patient's oncologist, a restaging FDG PET/CT will be obtained at > 10 weeks following the start of pembrolizumab. This exam is clinical standard of care for restaging of disease after initiation of a new line of therapy, and would be performed even if the patient was not enrolled in the study. In some cases MRI or CT imaging may be performed as standard of care for restaging disease instead of FDG PET/CT.

[figure not shown]
Almost all of the patients treated for melanoma in the University of Pennsylvania Health System (UPHS) have consented to participate in the Penn Melanoma Tissue Collection Program (UPCC #08607, IRB #703001). For patients participating in this program, blood samples will be collected, processed, and stored according to the program's standard operating procedure. Currently, this includes drawing less than 65 mL of blood according to the following schedule (after initiation of pembrolizumab): weeks 0, 3, 6, 9, 12, 15, and at 1 year. For the purposes of this study, patients will have an additional sample of blood drawn at approximately 1 week after starting pembrolizumab; this sample will also be collected, processed, and stored according to the Penn Melanoma Tissue Collection Program standard operating procedure. If patients have not consented to participate in the Penn Melanoma Tissue Collection Program, then no blood samples will be drawn for the purposes of this study. Analysis of blood samples will include, but is not limited to, analysis of serum cytokines, chemokines, and T cell markers. This data will be correlated to patient response as well as changes in tumor FDG uptake. Some of these studies will be performed upon receipt of additional funding. There may be patients for which some or all of these blood draws are not possible, in this case it will be documented in the CRF and the blood draws may be omitted and it will not be considered a protocol deviation. Experimental pathology results will not be reported to the participant and will have no impact on the treatment decisions made by the treating physician.

Patients may undergo tumor biopsy as part of their clinical care prior to initiation of pembrolizumab. For patients participating in the Penn Melanoma Tissue Collection Program, these pre-therapy tissue samples will be collected, processed, and stored according to the program's standard operating procedure. For the purposes of this study, patients will have a post-therapy tumor biopsy which will be scheduled within 7 days after the 1st Post-therapy FDG PET/CT; this tissue will also be collected, processed, and stored according to the Penn Melanoma Tissue Collection Program standard operating procedure. If patients have not consented to participate in the Penn Melanoma Tissue Collection Program, then no tumor biopsies will be performed for the purposes of this study. The biopsy techniques preferred for this study include core biopsies or surgical biopsies. The same biopsy techniques should be used as routinely used for a given tumor lesion/location. When possible, the

post-therapy tumor biopsy should target the same lesion that was biopsied pre-therapy; if the original lesion cannot be biopsied, then a lesion with a significant change in FDG activity should be targeted for biopsy. Analysis of tissue samples will include, but is not limited to, analysis of tumor-infiltrating lymphocytes (TILs) and macrophages. This data will be correlated to patient response as well as changes in tumor FDG uptake. Some of these studies will be performed upon receipt of additional funding. There may be patients for which a pre- or post- therapy tumor biopsy is not performed; those cases will be documented in the CRF and will not be considered a protocol deviation. In some cases tissue may be collected outside of the 7 day window following the 1st Post-therapy FDG PET/CT; this will not be considered a protocol deviation. Experimental pathology results will not be reported to the participant and will have no impact on the treatment decisions made by the treating physician.

For patients participating in the Penn Melanoma Tissue Collection Program, we will follow the standard operating procedure regarding archival tissue access for patients undergoing a biopsy or surgery on melanoma or other skin cancer for diagnosing, treating or research purposes, but for which there is no applicable left over fresh tissue, or patients who had a biopsy or surgical procedure done on melanoma or other skin cancer for diagnosing, treating or research purposes at the University of Pennsylvania Health System (UPHS) or at an institution outside of UPHS. If patients have not consented to participate in the Penn Melanoma Tissue Collection Program, then no archival tissue will be requested.

2.2 Trial Diagram

¹ Pembrolizumab therapy will be given as part of the standard clinical care as determined by the treating oncology team. The blood draw at 1 week will be performed only if the patient is participating in this study and has also agreed to participate in the Penn Melanoma Tissue Collection Program, and may be omitted if it cannot be collected. The patient will remain evaluable for the primary endpoint even if the blood draw is omitted.

² Tumor tissue will be collected, processed, and stored according to the Penn Melanoma Tissue Collection Program standard operating procedure. If patients have not consented to participate in the Penn Melanoma Tissue Collection Program, then a tumor biopsy will not be performed for the purposes of this study. In some patients the tumor biopsy may not be performed, or may be performed outside of the 7 day window following the Research FDG PET/CT; omission/delay of the tumor biopsy will not be considered a protocol deviation.

³ The 2nd Post-Therapy scan will be ordered as a clinical restaging scan. In some cases MRI or CT imaging may be performed as standard of care for restaging disease instead of FDG PET/CT.

3.0 OBJECTIVES & HYPOTHESES

3.1 Primary Objectives & Hypotheses

(1) **Objective:** To determine the distribution of changes from baseline in tumor FDG uptake on PET/CT at 3 weeks and >10 weeks after initiation of pembrolizumab.

Hypothesis: None, descriptive statistics.

(2) **Objective:** To evaluate the ability of FDG PET/CT to serve as an early measure of objective response to therapy in patients with melanoma on pembrolizumab.

Hypothesis: Melanoma metastases demonstrate changes in FDG uptake on a 3 week PET/CT scan that are associated with objective response to pembrolizumab.

3.2 Secondary Objectives & Hypotheses

(1) **Objective:** Based on changes in tumor FDG uptake at 3 weeks, determine which patients have FDG “flare” (an early increase in tumor FDG PET/CT uptake), and assess whether FDG “flare” is predictive of progression-free survival and overall survival in patients with melanoma on pembrolizumab.

Hypothesis: A flare response on FDG PET/CT performed 3 weeks after initiation of pembrolizumab is predictive of progression-free survival and overall survival in patients with melanoma.

(2) **Objective:** To collect tumor tissue pre- and post- treatment with pembrolizumab for correlation with changes in FDG uptake and objective response to therapy, and for studies of mechanism of action of PD-1 blockade with pembrolizumab.

Hypothesis: Treatment with pembrolizumab will result in a measurable change in tumor immune biomarkers, which will correlate with changes in tumor FDG uptake (including a “flare” response) and objective response to therapy, and will contribute to a better understanding of the mechanism of action of pembrolizumab.

(3) **Objective:** To measure immune biomarkers in blood from subjects before and at serial time points after treatment with pembrolizumab, for correlation with changes in FDG uptake and objective response to therapy, and for studies of mechanism of action of PD-1 blockade with pembrolizumab.

Hypothesis: Treatment with pembrolizumab will result in a measurable change in blood immune biomarkers, which will correlate with changes in tumor FDG uptake (including a “flare” response) and objective response to therapy, and will contribute to a better understanding of the mechanism of action of pembrolizumab.

(4) **Objective:** To correlate changes in tumor FDG uptake (including a “flare” response), serum immune biomarkers, and tissue immune biomarkers with objective response to therapy, progression-free survival, and overall survival. Changes in FDG uptake within immune related tissues (lymph nodes, spleen, bone marrow, and thymus) will also be correlated with serum and tissue immune biomarkers, and response.

Hypothesis: Serum and tissue immune biomarkers provide additional predictive value regarding objective response to therapy, progression-free survival, and overall survival when combined with FDG PET/CT imaging data.

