It has recently been recognized that immune activation results in a similar cellular metabolic switch from oxidative phosphorylation to aerobic glycolysis. This occurs with both the innate and adaptive immune activation. For example, when activated using TLR ligands or pro-inflammatory cytokines, neutrophils, dendritic cells, and macrophages have been demonstrated to switch their metabolism from oxidative phosphorylation to aerobic glycolysis.⁵ Similarly, following TCR stimulation, lymphocytes increase glucose utilization by several orders of magnitude and switch glucose metabolism from oxidative phosphorylation to aerobic glycolysis.^{6,7} Interestingly anti-inflammatory subpopulations of both the innate and adaptive immune system, such as M2 macrophages, regulatory T cells and quiescent memory T cells, demonstrate a predominant use of oxidative phosphorylation rather than aerobic glycolysis as opposed to their inflammatory counterparts such as activated macrophages and T-helper 17 cells.⁸

The upregulation of aerobic glycolysis in immune activation is readily visualized with FDG PET/CT imaging. Inflammatory conditions such as infection, rheumatoid arthritis and sarcoidosis yield intense avidity for FDG that compares with or exceeds that of most malignancies.^{9,10} In fact, a significant limitation to the use of FDG PET/CT in cancer restaging has been interference of the tumor FDG signal by post-therapeutic inflammatory tissues including surgical changes, talc pleurodesis, and radiation therapy.¹¹

In this study we propose utilizing FDG PET/CT to assess the immunotherapy response by detecting the superimposed increased metabolism within the tumor presented by a therapy-induced infiltrating population of glucose avid activated immune cells. Of note, a flare

phenomenon has been described in several cancer types following therapy; in patients with breast cancer on endocrine therapy, a clinical flare response was identified in 4 of 17 responders and 1 of 34 nonresponders, and an FDG PET flare response was seen in 15 of 17 responders and none of the 34 nonresponders.¹² These results suggest that FDG PET is more sensitive and specific for detecting a flare response compared to clinical criteria, and the results also suggest that a flare response is predictive of response to therapy.

FDG PET/CT studies are typically performed at approximately 12 weeks following the initiation of

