8.0 STATISTICAL CONSIDERATIONS

8.1 Design:

This is a pilot correlative study for patients with metastatic melanoma receiving pembrolizumab on a standard regimen. The intent of this study is to evaluate FDG PET/CT as an early measure of response to immunotherapy. Tumor FDG uptake will be measured at baseline and at 3 and >10 weeks after initiation of pembrolizumab. 30 evaluable patients will be enrolled; evaluable implies that the patient had baseline and week 3 FDG PET/CT scans. This study will also include serum and tissue sampling for immune biomarkers.

8.2 Objectives:

The primary objectives are to:

1. Determine the distribution of changes from baseline in tumor FDG uptake on PET/CT at 3 weeks and >10 weeks after initiation of pembrolizumab.
2. Test for the association between change in tumor FDG uptake on PET/CT at 3 weeks and objective response (RECIST).

The secondary objectives are to:

1. Based on change in FDG uptake at 3 weeks, determine which patients have FDG “flare.”
2. Test for the association between FDG flare (yes/no) and objective response.
3. Test for the association between FDG flare and progression-free and overall survival.
4. Test for correlation between change in FDG uptake and levels of immune biomarkers in serum and tissue.
5. Test for association between changes in immune biomarkers in serum and tissue with objective response, progression-free survival, and overall survival.

8.3 Endpoints:

1. Objective response is defined by RECIST. The clinical evaluation takes place at 3 months per standard pembrolizumab regimens. Patients will be categorized as responders (complete response or partial response) or nonresponders (stable disease or progressive disease).

2. The maximum standardized uptake value (SUVmax) will be analyzed for all tumor sites. Immune-related tissues will be analyzed with SUVmax and SUVmean.
3. Studies have shown that the baseline test/re-test variability is 15-20%. Thus, FDG “flare” will likely be defined by >20% increase in tumor FDG uptake at 3 weeks. This definition may be modified for the observed distribution of changes in tumor FDG uptake on our study.
4. Progression-free and overall survival are defined in Section 4.1.2.
5. Immune biomarkers (see Section 7.1.2.3).

8.4 Plans for Data Analysis:

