This is a pilot correlative study of FDG PET/CT imaging to evaluate early response to immunotherapy. We will first begin with a descriptive analysis. For continuous variables, we will generate graphs and descriptive statistics (e.g., means, standard deviations, medians and inter-quartile range). Categorical variables will be described by frequencies, proportions and 95% exact confidence intervals. Change in tumor FDG uptake will be closely examined. It is likely that change in tumor SUVmax >20% will be classified as a FDG “flare” and the number of patients with a flare will be computed.

Next, associations between change in tumor FDG uptake with clinical outcomes will be conducted. Change in tumor FDG uptake at 3 weeks will be compared between responders and nonresponders by a two sample t-test. Also, objective response rates will be compared between patients with or without FDG “flare” by Fisher’s exact test.

PFS and OS will be estimated by the method of Kaplan and Meier. Median values and 95% confidence intervals will be calculated. PFS and OS will be compared between patients with or without FDG “flare” by the log rank test. Cox regression may be used to assess the effect of continuously scaled measurements of FDG change. For all survival analyses, a landmark analysis will be performed. Here, PFS or OS are defined from a landmark, which is 3 weeks after initiation of pembrolizumab. The landmark method is necessary because the change in tumor FDG uptake is known at 3 weeks. Serum and tissue biomarkers will be correlated with change tumor FDG uptake, using Pearson correlation or Spearman’s correlation, as appropriate. Within-patient pre-/post-treatment changes in biomarkers will be evaluated by paired Student’s t-test or Wilcoxon signed ranks test, as appropriate. We will test for an association between post-/pre-treatment fold change in immune biomarkers in serum and tissue and objective response, progression-free survival, and overall survival using logistic regression (for response) and Cox regression (for time-to-event outcomes) using landmark survival analysis.

8.5 Sample Size Justification:

The target is 30 evaluable patients, which may require up to 35 enrolled patients. Based on our clinical experience, we assume a 50% objective response rate, thus there will be 15

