responders and 15 nonresponders. A comparison of change in FDG SUV at 3 weeks between responders and nonresponders, will have 84% power to detect a 1.0SD difference in mean values, using 1-sided two sample t test at a 5% significance level. The 1-sided test is justified, since responders are expected to have greater changes in FDG SUV.

8.6 Study Duration:

This study will enroll 30 evaluable patients over 1 year.

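### If few patients show a flare, the usual log-rank p-value for PFS and OS is skewed against the expected direction; Section 8.4 should name a tail-specific permutation version and state level and sidedness

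*Combined protocol and SAP*

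**What the plan says.** The hypothesis under the first secondary objective in Section 3.2 reads "A flare response on FDG PET/CT performed 3 weeks after initiation of pembrolizumab is predictive of progression-free survival and overall survival". It gives no direction. One can be inferred from Section 4.1, which cites an FDG PET study in breast cancer and concludes that "the results also suggest that a flare response is predictive of response to therapy".

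Section 8.4 gives the test: "PFS and OS will be compared between patients with or without FDG “flare” by the log rank test". Time runs from a landmark: "PFS or OS are defined from a landmark, which is 3 weeks after initiation of pembrolizumab". The sample is small by design (Section 8.1: "30 evaluable patients will be enrolled; evaluable implies that the patient had baseline and week 3 FDG PET/CT scans"), and anyone with an event before the landmark drops out of the comparison. For flare against response, the same section chooses an exact method: "objective response rates will be compared between patients with or without FDG “flare” by Fisher’s exact test".

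The only level and sidedness in the plan belong to the primary comparison in Section 8.5 ("using 1-sided two sample t test at a 5% significance level"). For the log-rank test there is no level, sidedness, reference distribution, expected flare count, event count or power. Section 8.3 also allows the 20% cut for flare to be changed once the data are seen.

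**The concern.** A log-rank test with no further qualification is normally read from a chi-square table, which is a large-sample approximation. It works well with balanced groups and poorly when one group has only a few patients. Flare status is observed, so nothing in the design keeps the groups balanced. The plan guards against small cells when flare is compared with response, but not when the same two groups are compared on survival.

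If flares are few, a chance finding that flare predicts worse survival becomes more likely than the nominal level suggests. A real survival advantage with flare, which the rationale leads one to expect, is missed more often than it need be.

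**Working it through.** **The plan's own figure.** The only power statement is for the primary t-test: 15 against 15, 1.0 SD, one-sided 5%, 84%. The noncentrality is 1.0 × √(15 × 15 / 30) = √7.5 = 2.74 on 28 df, which gives 84.8%, so it reproduces. There is no figure for the log-rank test to reproduce.

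**How many flares?** The plan does not say. Section 4.1 reports a PET flare in 15 of 17 responders and 0 of 34 nonresponders in breast cancer. Section 8.5 assumes 15 responders, so the analogy implies 15 × 15/17 = 13.2 flares, or 44% of 30. The chance of 5 or fewer flares in 30 (binomial) is 93% at an assumed flare rate of 10%, 43% at 20%, 8% at 30% and 0.2% at 44%.

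**Why the statistic is skewed.** Take 3 flares in 30, 15 events, and no censoring before the last event. The best result for flare is no event in that group. Then
- E = Σ 3/k for k = 16 to 30 = 2.03
- V = Σ (3/k)(1 − 3/k) = 1.74
- Z = −2.03/√1.74 = −1.54.

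Even the best result cannot reach −1.96. If the 3 flare patients have the first three events, O − E = 2.80, V = 0.19 and Z = +6.4. The two tails are far from symmetric.

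**Null error of the chi-square log-rank test.** Simulation with n = 30, exponential times, uniform censoring, nominal two-sided 5% (2.5% per tail) and 150,000 datasets per cell. The event fractions are assumptions. Entries are total error (flare-worse tail / flare-better tail), in %.

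| Flares | 50% events | 77% events | 100% events |
|---|---|---|---|
| 3 | 6.5 (6.3 / 0.2) | 8.5 (7.4 / 1.1) | 8.7 (7.4 / 1.4) |
| 4 | 6.0 (5.4 / 0.6) | 7.4 (6.2 / 1.3) | 7.9 (6.3 / 1.6) |
| 6 | 5.8 (4.4 / 1.4) | 6.4 (4.7 / 1.6) | 7.1 (5.2 / 1.9) |
| 8 | 5.5 (3.8 / 1.7) | 6.0 (4.1 / 1.9) | 6.5 (4.4 / 2.1) |
| 13 | 5.3 (2.9 / 2.4) | 5.6 (3.1 / 2.5) | 6.0 (3.3 / 2.7) |
| 15 | 5.3 (2.6 / 2.7) | 5.5 (2.7 / 2.8) | 6.0 (3.0 / 3.0) |

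At about 33% events the total is 5.0-5.3% from 4 flares upwards, but the skew stays (4 flares: 5.2 / 0.1).

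**If the test is one-sided 5% towards flare being better**, error at 50-100% events is 1.8-3.1% with 3 flares and 3.6-4.1% with 6. No false-positive excess arises.

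**Does a permutation test help?** It depends on how the p-value is formed. With 77% events under the null, permuting |Z| gives total error 4.7%, 4.7% and 5.5% at 4, 6 and 10 flares, but the skew remains: the flare-better tail is 0.6% at 4 flares. Taking each tail at 2.5% separately gives flare-better / flare-worse tails of 2.4 / 2.3%, 3.2 / 2.6% and 2.6 / 2.8% (2,000 datasets, standard error √(0.025 × 0.975 / 2000) = 0.35 points).

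Power when flare is truly better, two-sided 5%:

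| Flares, HR | Chi-square | Permutation, each tail separately | Permutation of absolute Z |
|---|---|---|---|
| 4, HR 0.3 | 26% | 35% | 16% |
| 6, HR 0.3 | 41% | 49% | 35% |
| 10, HR 0.3 | 59% | 62% | 57% |
| 6, HR 0.4 | 26% | 32% | 21% |
| 8, HR 0.4 | 34% | 39% | 31% |

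The HR 0.3 rows use the censoring that gives 77% events under the null; the HR 0.4 rows have about 70% events. The hazard ratios are illustrative and not from the plan.

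**The case against.** The strongest reply is that the harm is conditional and modest. The plan's PET analogy points to about 13 flares, where the chi-square test is nearly correct. This stands, and it limits the point to the case of a small flare group.

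A reader might take the 3.6% flare rate in Section 4.1 as a lower bound, about 1 of 30. The documents do not support that. The figure is for a 25% or greater increase in tumour burden at 12 weeks, and the plan cites it to explain why it images earlier. It is not an estimate of the 3-week SUVmax flare rate.

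The level and direction are not in the plan either. If the one-sided 5% of Section 8.5 were carried over towards flare being better, only the loss of power would remain. Section 8.4 also does not exclude an exact p-value; the chi-square version is an inference from usual practice.

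Finally, this is a secondary analysis in a pilot with no power claim for survival. Kaplan-Meier curves, medians with confidence intervals and an optional Cox model on continuous FDG change are already planned. Even with 15 against 15 and 77% events, power for HR 0.5 is only about 33%, so study size limits this hypothesis more than the reference distribution does. All of this lowers the priority. It does not remove the reason to name the method in advance, because the split is unknown until the scans are read.

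**Conclusion.** The point holds in conditional form and is minor. With about 3 to 8 flares among 30, and 50-100% events, the chi-square log-rank test at a nominal two-sided 5% has a true error of about 5.5-9%. The flare-worse tail is about 4-7% and the flare-better tail 0.2-2.1%, against 2.5% each. With about 13 flares the error is about 5-6% with little skew.

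It would be tempting to say that the planned test has an error above 5%, or that a false finding of harm is three times as likely as it should be. The ratio 7.4/2.5 = 3.0 arises only at 3 flares and only on a two-sided reading, and the documents give neither the flare count nor the sidedness.

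The figures assume exponential times, uniform censoring unrelated to flare, and no patients lost before the landmark.

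**What to change.** In Section 8.4:

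- State the level and sidedness of the PFS and OS comparisons by flare status.
- Keep the Kaplan-Meier curves and the log-rank statistic, but take the p-value from the permutation distribution of the signed log-rank Z. Permute flare labels among the patients at risk at the landmark, by full enumeration or at least 10,000 permutations. With 3 flares, enumeration needs only 30 × 29 × 28 / 6 = 4,060 arrangements.
- For a two-sided test, use twice the smaller tail probability. Do not permute |Z| or the chi-square value.
- Report the flare-group size, and events and censoring by group.

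The cost is two or three sentences and a few lines of code, with no extra data. The test assumes similar censoring in the two groups, which the reported censoring lets a reader judge. With balanced groups the loss is negligible: at 15 against 15, 50% events under the null and HR 0.3, holding each tail at 2.5% changes power from 44.5% to 43.7%. With a single flare the smallest possible two-sided p-value is 2 × 1/30 = 6.7%, so that case can only be described.

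### Secondary hypothesis 4 claims that biomarkers add predictive value to FDG PET/CT, but Section 8 specifies no outcome model containing both, so the hypothesis cannot be tested as planned

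*Combined protocol and SAP*

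**What the plan says.** Section 3.2 sets an objective and a hypothesis under item 4. The objective is correlational: "To correlate changes in tumor FDG uptake (including a “flare” response), serum immune biomarkers, and tissue immune biomarkers with objective response to therapy", and likewise with the survival endpoints. The hypothesis goes further, predicting that the blood and tumour markers will "provide additional predictive value regarding objective response to therapy, progression-free survival, and overall survival when combined with FDG PET/CT imaging data".

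Section 8.2 turns this into a narrower statistical objective that does not mention FDG: "Test for association between changes in immune biomarkers in serum and tissue with objective response, progression-free survival, and overall survival".

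Section 8.4 then gives the methods. On biomarkers and outcome: "We will test for an association between post-/pre-treatment fold change in immune biomarkers in serum and tissue and objective response", with PFS and OS also named, "using logistic regression (for response) and Cox regression (for time-to-event outcomes) using landmark survival analysis". No covariates are listed. The only planned analysis linking biomarkers to FDG has no outcome in it: "Serum and tissue biomarkers will be correlated with change tumor FDG uptake, using Pearson correlation" or Spearman's coefficient.

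Hypotheses 2 and 3 in Section 3.2 predict that treatment will change tissue and blood biomarkers, "which will correlate with changes in tumor FDG uptake (including a “flare” response) and objective response to therapy".

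**The concern.** Added value is a conditional question: once the FDG change is known, does the marker still tell us something about outcome? Answering it needs both quantities in the same outcome model, or some other incremental measure such as a change in discrimination. Section 8 has neither.

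The gap matters more here than it would for unrelated predictors, because the protocol itself expects markers to track FDG change and FDG change to track response. If both hold, a marker carrying no information beyond FDG will inherit some association with response. An investigator who holds a significant marker-response result and a hypothesis worded as additional value could report the first as support for the second.

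**Working it through.** **1. What each planned analysis can answer (Section 8.4)**

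| Planned analysis | FDG change | Biomarker | Outcome |
|---|---|---|---|
| t-test, Fisher, log rank, Cox on FDG change or flare | yes | no | yes |
| Pearson or Spearman correlation | yes | yes | no |
| Logistic and landmark Cox on biomarker fold change | not stated | yes | yes |
| Needed for hypothesis 4 | yes | yes | yes |

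No specified analysis fills the last row.

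**2. The plan's own figure.** Section 8.5 gives 84% power for a 1.0 SD difference in FDG change, 15 against 15, one-sided t-test at 5%. With 28 degrees of freedom and noncentrality 1/√(2/15) = 2.74, the exact power is 84.8%. The figure reproduces. It covers the FDG-response comparison only; the plan gives no figure for added value.

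**3. Size of the problem for response.** From Section 8.5: 15 responders, 15 nonresponders, FDG difference 1.0 within-group SD. Assumed: the within-group marker-FDG correlation r. The illustrative marker has no independent effect:

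marker = r × FDG + √(1 − r²) × noise.

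Its within-group variance is r² + (1 − r²) = 1, so its standardised difference between responders and nonresponders is r × 1.0 = r. A rough two-sided 5% rejection rate for the marker by itself follows from noncentrality k = r × 2.74:

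Φ(k − 1.96) + Φ(−k − 1.96).

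Simulated likelihood-ratio tests in logistic regression (two-sided 5%) give the last two columns.

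| r (assumed) | k | Normal approximation, marker by itself | Simulated, marker by itself | Simulated, marker added to FDG |
|---|---|---|---|---|
| 0.2 | 0.55 | 8.5% | about 9% | about 6-8% |
| 0.4 | 1.10 | 19.5% | about 21% | about 6-8% |
| 0.6 | 1.64 | 37.6% | about 38% | about 6-8% |
| 0.7 | 1.92 | 48.3% | about 50% | about 6-8% |

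The hand approximation and the simulation agree. The last column sits slightly above 5% because the likelihood-ratio test is a little liberal in small samples.

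**4. What the joint model can deliver.** For a marker with a 1 SD shift independent of FDG, simulated power of the joint test is about 66-68% at n = 30. For a 0.5 SD shift it is roughly one in four. At n = 20 the unpenalised test rejects a null marker in about 8-9% of studies; at n = 12, in about 11%.

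**5. Number of candidates.** Table 1 lists 6 + 8 + 3 = 17 cytokines and chemokines. Table 2 lists 7 + 2 + 2 + 9 + 3 = 23 flow markers. That makes 40 proposed markers against about 15 responders.

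**The case against.** The strongest reply is that the plan is silent rather than wrong. Section 8.4 names logistic and Cox regression without listing covariates, so a joint model is not excluded. A reader might infer that the plan commits to testing each biomarker in isolation. The text does not say so; it supports only the statement that no joint model is specified. This stands.

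A reader might also infer that the study would wrongly declare added value. The documents contain no rule turning a marker-outcome p-value into such a claim, Section 8.2 speaks only of association, and the planned marker-FDG correlation would reveal a marker that tracks FDG. So the risk is that a marker could be credited, not that it will be. The correlation does not close the gap, however: overlap with FDG neither proves nor disproves added value.

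Nor would every correlated marker look predictive. At r = 0.2 the problem is small, and at no listed correlation below 0.7 does the marker reach significance in as many as half of studies.

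The mirror-only marker is also a chosen scenario. The rationale in Section 4.1 treats immune infiltration as the source of the FDG signal, so some markers may carry information that FDG lacks. That limits the simulation to an illustration, but whether they do is exactly what only a joint model can address.

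Finally, this is a pilot, and the sample can barely support two-predictor models. That is a fair reason to call the result exploratory or to soften the hypothesis. It is not a reason to leave an incremental hypothesis without an analysis.

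**Conclusion.** The mismatch is real and modest. Hypothesis 4 asserts added value, and nothing specified in Sections 8.2 or 8.4 tests it. Under the plan's own group sizes and FDG effect, a marker with no independent effect would be significant by itself in about 9% to 50% of studies for assumed within-group correlations of 0.2 to 0.7, against about 6-8% with FDG change in the model.

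These figures rest on the assumed correlations, on a marker related to response only through FDG, on complete samples in 30 patients, and on the response endpoint; PFS and OS were not simulated. The conclusion that the hypothesis lacks a matching analysis rests on none of these. The point concerns one secondary hypothesis. It leaves the primary objectives and the 84% power figure untouched.

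**What to change.** In Section 8.4, name a short list of markers in advance. For each:

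- Fit response by Firth-penalised logistic regression with 3-week FDG change and the marker. Prespecify the penalty rather than adopting it only once separation is seen.
- Fit landmark PFS and OS by Cox regression with the same two terms, using only markers sampled by the landmark.
- Test the marker by likelihood ratio (penalised for response) against the model with FDG change only. Report its estimate and confidence interval, and label the result exploratory.
- Base any statement of additional value on this joint model, not on the marker-outcome association.

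State how many patients have the samples needed for each model. If too few do, restrict the conclusion and reword hypothesis 4 to association, which is what objective 4 and Section 8.2 already say.

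The cost is SAP wording and one extra covariate per model, with no new visits, patients or data. The downside is wide intervals and modest power at n = 30 or fewer. Sections 2.1 and 7.1.2.3 allow biopsies and blood draws to be omitted, make both depend on consent to the separate tissue collection programme, and leave some of the laboratory studies dependent on further funding. The plan should say so.
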